4.3 Follow-up period

4.3.1 Safety follow-up visit, 4 weeks after Day 70 visit

Patients will arrive at the study site for a safety follow-up visit. Assessments for the follow-up visit are outlined in [Table 2](#).

Samples will be taken from patients for safety laboratory assessments. See [Table 4](#) for a list of the safety laboratory variables.

At this visit, IVRS/IWRS should be contacted to document study completion.

Note: other treatments during the 4 weeks of follow-up after Day 70 can be initiated.

4.4 Early termination visit

For patients who are discontinuing the study, the last study visit will serve as the early termination visit, with assessments as outlined in [Table 2](#). The IVRS/IWRS should be contacted to discontinue the patient.

Blood samples for PK and biomarker analysis will be collected according the following schedule:

- Perform PK blood sampling, prior to the meal, if performed on a standardized breakfast meal PPGT test day (see [Section 5.4](#)).
- Collect blood samples for biomarker analysis, prior to the meal, if performed on a standardized breakfast meal PPGT test day (see [Section 5.7](#)).

Samples will be taken from patients for FPG, HbA1c, and safety laboratory assessments. See [Table 4](#) for a list of the safety laboratory variables.

All study medication will be collected, and the patient's compliance with study medication and open-label metformin XR based on pill count and with study medication (based on single dosing trays, returned kits and drug accountability forms) will be assessed and recorded on the eCRF.

If the patient discontinues during one of the 7 day CGM periods, remove CGM device. The CGM device should not remain in place longer than 10 days.

If the patient is discontinuing the study due to an adverse event, a blood sample will be collected for assessment of exenatide plasma concentration.

Follow-up care for patients discontinuing the study should be discussed.

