1.4 Study design

This will be a randomized, double-blind, parallel-group study comparing EQW vs. placebo in patients with T2DM treated with metformin XR. The patient population will consist of male and female patients ≥ 18 years and ≤ 75 years of age, inclusive, with T2DM who have inadequate glycemic control (HbA1c $\geq 7\%$ and $\leq 10\%$ at screening) who have been receiving a stable dose of metformin (≥ 1500 mg/day) for at least 8 weeks. Approximately 110 patients will be randomized in a 1:1 ratio (EQW:placebo) to achieve approximately 55 patients per treatment arm. After the 4-week lead-in period, patients will be randomized and then treated for 10 weeks. Following 10 weeks of treatment, standard safety assessments will be assessed during a 4-week follow-up period.

A continuous glucose monitoring (CGM) system will be used to measure the patient's interstitial glucose level. The 7 day assessment using the CGM will be performed during the lead-in period (Day -8 to Day -1), and during the Treatment Period (Day 21 to Day 28 and Day 63 to Day 70). The glucose measurements used for assessment of the primary endpoint will be analyzed from the CGM data.

A flow chart of the study design is provided in [Figure 1](#).

Figure 1 Study flow chart

- a) Patients with T2DM, on stable dose of metformin XR (≥ 1500 mg/day), and inadequate glucose control: HbA1c $\geq 7\%$ and $\leq 10\%$.
 - b) Enter the single-blind medical nutrition and metformin XR lead-in phase.
 - c) Patients will undergo a 7-day CGM assessment during the lead in period (Day -8 to -1)
 - d) Patients will be randomized 1:1 to receive either EQW + open-label metformin XR (1500-2000 mg) OR placebo + open-label metformin XR (1500-2000 mg) once weekly.
 - e) Upon completion of the lead-in period, eligible patients will enter the 10-week, double-blind treatment period, followed by a 4-week follow-up period for safety assessments. All patients will undergo CGM blood glucose monitoring, for interstitial glucose from Day 21 to Day 28 and from Day 63 to Day 70.
 - f) The safety assessments will be collected at a 4-week follow-up visit.
- CGM = continuous glucose monitoring; EQW = exenatide once weekly; HbA1c = hemoglobin A1c; Met = metformin; T2DM = type 2 diabetes mellitus.

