3.9.1.2 Discontinuation due to elevated serum creatinine

During the lead-in period, patients with a Scr ≥ 1.5 mg/dL (132.6 $\mu\text{mol/L}$) in males or ≥ 1.4 mg/dL (123.8 $\mu\text{mol/L}$) in females will be discontinued from the study.

- During the double-blind treatment period, patients with a Scr ≥ 1.5 mg/dL (132.6 $\mu\text{mol/L}$) but < 2.0 mg/dL (176 $\mu\text{mol/L}$) in males or ≥ 1.4 mg/dL (123.8 $\mu\text{mol/L}$) but < 2.0 mg/dL (176 $\mu\text{mol/L}$) in females, will have their open-label metformin XR held and a confirmatory repeat Scr drawn within 1 week. If the repeat Scr is ≥ 1.5 mg/dL (132.6 $\mu\text{mol/L}$) in males or ≥ 1.4 mg/dL (123.8 $\mu\text{mol/L}$) in females, the patient must be immediately discontinued from the study, AstraZeneca notified, and an early discontinuation visit performed which will include samples for the assessment of plasma concentrations. If the repeat Scr is < 1.5 mg/dL (males) or < 1.4 mg/dL (females), study medication may be resumed unless otherwise contraindicated.
- During the double-blind treatment period, patients (males and females) with a Scr ≥ 2.0 mg/dL (176 $\mu\text{mol/L}$), will have both blinded study medication and open-label metformin XR held and a confirmatory repeat Scr drawn within 1 week. If the repeat Scr is ≥ 1.5 mg/dL (132.6 $\mu\text{mol/L}$) in males or ≥ 1.4 mg/dL (123.8 $\mu\text{mol/L}$) in females, the patient must be immediately discontinued from the study, AstraZeneca notified, and an early discontinuation visit performed which will include samples for plasma concentrations. If the repeat Scr is < 1.5 mg/dL (males) or < 1.4 mg/dL (females), study medication may be resumed unless otherwise contraindicated.

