Patients are to arrive at their study visit prior to 18:00 on Day 70. Study procedures will be performed as listed in Table 2.

The IVRS/IWRS should be notified if the patient is discontinued from the study. Patients will remain at the study site for collection of PK and biomarker blood samples according to the sampling described below:

- Perform PK blood sampling (see Section 5.4).
- Collect blood samples for biomarker analysis (see Section 5.7).

Additionally, samples will be taken from patients for FPG, HbA1c, and safety laboratory assessments. See Table 4 for a list of the safety laboratory variables.

At the conclusion of the CGM monitoring on Day 70, the CGM device will be removed.

All study medication will be collected, and the patient's compliance with study medication and open-label metformin XR based on pill count and with study medication (based on single dosing trays, returned kits, and drug accountability forms) will be assessed and recorded on the eCRF.

Prior to leaving the study site at the end of visit on Day 70, the patient will be scheduled for a 4-week follow-up visit.

Patients will be reminded about fasting requirements (at least 8 hours) prior to the follow-up visit.

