6.3 Recording of adverse events

6.3.1 Time period for collection of adverse events

Adverse events will be collected from time of signature of informed consent throughout the treatment period and including the follow-up period.

Serious adverse events will be recorded from the time of informed consent up to 30 days after the last dose of study drug.

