8.2 Sample size estimate

Approximately 110 patients are expected to be randomized 1:1 to the EQW + metformin XR and placebo + metformin XR treatment arms (55 patients per treatment arm). The assumed dropout rate (30%) was based on a similar study (SHOT study; 20%), and increased by 10% as the present study is of longer duration, with a more demanding visit schedule. Therefore, a minimum of 39 patients per treatment arm would provide the necessary statistical power.

With 39 patients per treatment group, there is a 90% power to detect a difference in change in 24-hour mean weighted glucose of 18 mg/dL at Week 4 between exenatide once weekly and placebo, assuming an SD of 24 mg/dL. As the plasma exenatide concentrations are expected to continuously increase and achieve steady-state around Week 7-8, the treatment effect on glycemic control will be increased, therefore, it is expected that 39 patients per treatment group will provide >90% power for the Week 10 treatment comparison. With this sample size, there is approximately 83% power to detect a treatment difference in change in FPG of 30 mg/dL, assuming an SD of 45 mg/dL, and approximately 80% power to detect a difference in change in 24-hour mean weighted glucose of 32 mg/dL between treatments, assuming an SD of 50 mg/dL.

The above power calculation is based on a 2-sided t-test at $\alpha=0.05$. Family-wise Type I error will be controlled at 0.05 for primary and secondary endpoints by applying a sequential testing process. The hierarchical order is defined in Section 8.5.2.

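### Patients who discontinue early have no dated safety contact after the early termination visit, although SAEs are to be recorded to 30 days after the last dose

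*Protocol*

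**What the plan says.** The follow-up visit is anchored to completion of treatment wherever the protocol describes it:

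- Section 1.4 gives the design: "Following 10 weeks of treatment, standard safety assessments will be assessed during a 4-week follow-up period".
- Section 4.2.9 (Day 70, Visit 14) does the booking: "Prior to leaving the study site at the end of visit on Day 70, the patient will be scheduled for a 4-week follow-up visit".
- Section 4.3.1 carries the title "Safety follow-up visit, 4 weeks after Day 70 visit" and adds: "At this visit, IVRS/IWRS should be contacted to document study completion".

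For those who stop early, Section 4.4 says: "For patients who are discontinuing the study, the last study visit will serve as the early termination visit". The IVRS/IWRS is then told that the patient is discontinued, and follow-up care is to be talked over with the patient. Note f to Table 2 places these patients' final safety panel at the end of their participation. Table 2 has a Follow-up column beside the ET column, without a day number and without stating who attends.

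The recording rule in Section 6.3.1 is not limited to completers: "Serious adverse events will be recorded from the time of informed consent up to 30 days after the last dose of study drug". The same section collects other AEs through the follow-up period.

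Some patients reach ET through the protocol's own safety rules. On a confirmed creatinine rise, Section 3.9.1.2 says "the patient must be immediately discontinued from the study, AstraZeneca notified, and an early discontinuation visit performed".

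**The concern.** The protocol sets a 30-day SAE window for everyone but plans the visit that would cover its later part only for patients who reach Day 70. After ET, an SAE in a discontinued patient enters the data only if someone happens to report it.

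This matters because discontinuers include patients removed for a safety signal. Section 1.1 lists renal failure among the potential risks of exenatide. A patient taken out for creatinine has no later creatinine scheduled in the trial data. Completers, by contrast, have AE review, vital signs and a laboratory panel about four to five weeks after the last dose. Section 8.5.5 summarises AEs by treatment group, so if the two arms discontinued at different rates, the depth of post-treatment ascertainment would differ between them.

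**Working it through.** **Inputs.** From Section 8.2: 110 patients, 55 per arm; 39 per arm needed; dropout 30%, built from 20% in a similar study plus 10 points; 18 mg/dL, SD 24 mg/dL, two-sided 0.05. From Section 6.3.1: a 30-day SAE window. From Section 7.2: weekly dosing. From Section 4.3.1: follow-up 4 weeks after Day 70. Assumed, because the protocol does not state it: the gap *g* in days from last dose to ET.

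**1. The plan's own figures.** SE = 24 × √(2/39) = 5.43; 18/5.43 = 3.31. A two-sided t-test with 76 df then has power 0.905, which agrees with the stated 90%. Dropout: 39/(1 − 0.30) = 55.7, so 56 against the stated 55; conversely 55 × 0.70 = 38.5. The figures are reproduced to within one patient per arm.

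**2. Patients concerned.**
- At 30%: 110 × 0.30 = 33. From the stated completers: 110 − 2 × 39 = 32 (29%).
- At the similar study's 20%: 110 × 0.20 = 22.

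**3. SAE days after the last planned contact** = 30 − *g*:

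| *g* (days) | Days left | Share of 30 |
|---|---|---|
| 0 | 30 | 100% |
| 3 | 27 | 90% |
| 7 | 23 | 77% |
| 14 | 16 | 53% |
| 15 | 15 | 50% |
| 21 | 9 | 30% |

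More than half the window is uncovered only while *g* is 14 days or less.

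**4. The creatinine case.** At 2.0 mg/dL or above, Section 3.9.1.2 holds blinded drug and asks for a repeat within a week. If the last weekly dose was up to 7 days before the first sample, *g* can reach 7 + 7 = 14, leaving 16 of 30 days.

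**5. Completers for comparison.** Follow-up falls on Day 70 + 28 = Day 98. After a last dose on Day 63 or 64 that is 35 or 34 days. If dosing on Day 7 of each week were read as including Day 70, it is 28 days.

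**6. The remedy.** A visit 4 weeks after ET falls *g* + 28 days after the last dose. For *g* = 0 or 1 that is Day 28 or 29 of the window, so a lower limit of 30 days from the last dose is also needed. With it, the uncovered days fall to 0.

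**The case against.** The protocol is not silent about patients after they stop:

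- Section 3.9.3 says AEs in patients who discontinue product are followed up.
- Section 6.3.2 has the investigator follow unresolved AEs as long as medically needed and lets the sponsor ask for more information.
- Section 6.3.6 makes a laboratory deterioration that leads to stopping product reportable as an AE, so the creatinine case is captured as an event.
- Section 3.9.2 requires a repeat sample and follow-up after liver elevations.
- Appendix D (Sections 4.2 and 5) has potential Hy's Law cases monitored until values return to normal or baseline, or as long as medically indicated, with dedicated CRF modules and a review within three weeks.

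This stands, and it limits the clinical gap. A reader might infer that hepatic outcomes in discontinuers go undocumented; for potential Hy's Law cases the documents say otherwise. For other events the provisions carry no date, and Section 6.3.2 works without further eCRF recording, so the gap in trial data remains.

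No sentence excludes ET patients from follow-up, and the Table 2 column could be read to include them. That also stands: the absence of a visit is the likelier reading of Sections 4.2.9, 4.3.1 and 4.4, not an explicit rule. Sites could resolve it differently, which is itself a reason to clarify.

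The size is soft. The 30% is a planning assumption, not an observed rate or a ceiling. It includes patients who withdraw consent, whose AE follow-up Section 3.10.2 places outside the study, and patients who cannot be reached. No visit is scheduled between Day 28 and Day 57, so *g* could be longer for someone stopping then.

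**Conclusion.** The point holds as a gap between a recording duty and the means to meet it: SAEs are due to 30 days after the last dose in all patients, but early discontinuers have no dated contact after ET. It concerns roughly 22 to 33 of 110 patients at dropout of 20% to 30%; the number an added contact would actually help is smaller and cannot be derived from the protocol. The uncovered part is 23 to 30 of 30 days if ET comes within a week of the last dose and 16 of 30 at two weeks; both rest on an interval that the protocol does not set.

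Two stronger readings are not supported. One is that 30% is an upper limit and that most of the window is always uncovered; at *g* of 15 days or more it is half or less. The other is that safety is under-ascertained specifically in the exenatide arm; the protocol gives a single dropout rate and no arm-specific expectation, so that remains conditional.

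The duty to record an SAE that comes to notice is intact. The issue is safety ascertainment only; the primary endpoint, its analysis and the sample size are untouched. It merits an amendment.

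**What to change.** Reconcile Sections 4.3.1, 4.4 and 6.3.1 and Table 2 so that the existing safety follow-up visit also applies to patients who discontinue early and have not withdrawn consent. Time it 4 weeks after the ET visit and no earlier than 30 days after the last dose. If the patient will not attend, make a telephone AE/SAE contact at the same time. State in Table 2 that the Follow-up column covers both groups.

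Keep the IVRS/IWRS discontinuation at ET as Section 4.4 now has it, and do not record these patients as study completers, because the Evaluable population in Section 8.3.1 depends on completion.

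The cost is amendment wording and a small number of extra visits or calls, some of which patients will decline. No dose, stopping rule or sample size changes.

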5. STUDY ASSESSMENTS

The electronic data capture (EDC) system will be used for data collection and query handling. The Investigator will ensure that data are recorded on the eCRF as specified in the study protocol and in accordance with the instructions provided.

The Investigator ensures the accuracy, completeness, and timeliness of the data recorded and of the provision of answers to data queries according to the Clinical Study Agreement (CSA). The Investigator will sign the completed eCRFs. A copy of the completed eCRFs will be archived at the study site.

5.1 Efficacy assessments

5.1.1 Primary efficacy assessment

5.1.1.1 Mean weighted glucose

The primary efficacy assessment will be the 24-hour mean weighted glucose which will be estimated by dividing the area under the 24-hour glucose curve (AUC_{0-24}) by 24 hours and will be expressed in mg/dL. Detailed calculation will be defined in the statistical analysis plan (SAP). The glucose measurements used for assessment of the primary endpoint will be analyzed from the CGM data.

5.1.2 Secondary efficacy assessments

5.1.2.1 Postprandial glucose

Secondary assessments including the 2-hour mean weighted PPG and 2-hour PPG, (2 hours after the breakfast meal) will be obtained during blood draws for glucose measurements after the standardized breakfast during the onsite monitoring visits on Day -7, Day 22, and Day 64 (3 day window) and will be processed at the central laboratory. The 2-hour mean weighted PPG will be estimated by dividing the area under the 2-hour glucose curve by 2 hours. Detailed calculation will be defined in the SAP.

5.1.2.2 Mean daily glucose

The mean daily glucose will be calculated based on the CGM data from a 3 day window of CGM. Each of the mean daily glucose measurements and meals should be performed and recorded at approximately the same time during the 3 days prior to the 24-hour monitoring visit. It is important to keep the consistency and timing of meals similar.

5.1.2.3 Fasting plasma glucose

Secondary efficacy assessments include the central laboratory measurement of FPG at Screening, Day -7, Randomization (Day 1), Day 15, Day 22, Day 57, Day 64, Day 70, and Early Termination (ET).

5.1.2.4 HbA1c

Assessment of HbA1c will be measured using the central laboratory measurement of HbA1c at Screening, Randomization (Day 1), Day 15, Day 22, Day 57, Day 64, Day 70, and ET.

5.1.2.5 MAGE, and the proportion of time patients who had plasma glucose measurements <70 mg/dL, ≥70 mg/dL, and ≤180 mg/dL, and >180 mg/dL

Mean amplitude of glucose excursion, and the proportion of time patients who had plasma glucose measurements <70 mg/dL, ≥70 mg/dL, and ≤180 mg/dL, and >180 mg/dL will be measured using the CGM system device. Mean amplitude of glucose excursion is calculated for each patient by taking the arithmetic mean of blood glucose increases or decreases (from blood glucose nadirs to peaks or vice versa) when both ascending and descending segments exceed the value of 1 SD of the blood glucose concentration in a 24 hour period.

5.2 Safety assessments

5.2.1 Laboratory safety assessments

Standard clinical laboratory tests, blood pressures and heart rate will be taken at the times indicated in the Study Plan (see [Table 2](#))

[Table 4](#) presents the laboratory safety variables measured for this study.

Table 4 Laboratory safety variables

Hematology	Clinical Chemistry (serum)
Hemoglobin	Creatine kinase (creatine phosphokinase) (CK) (CPK)
Hematocrit	Total bilirubin
Red blood cell count	Alkaline phosphatase (ALP)
White blood cell count and differential	Aspartate transaminase (AST, SGOT)
Platelet count	Alanine transaminase (ALT, SGPT)
	Amylase
	Lipase
Urinalysis	Total protein albumin
pH, protein, glucose, leukocyte esterase, blood by dipstick	Electrolytes – sodium, potassium, chloride
Microscopy if dipstick positive for blood, leukocyte esterase or protein	Serum creatinine (Scr), calculated creatinine clearance (Cockroft-Gault formula)
Urine HCG pregnancy test for WOCBP (HCG minimum sensitivity of 25 IU/L)*	Blood urea nitrogen (BUN)

*Note: If a urine HCG test is positive, a blood specimen will be obtained and a serum pregnancy test will be performed by the central laboratory for confirmation.

Additionally, a serum beta-HCG pregnancy test will be performed if necessary.

The Investigator should make an assessment of the available results with regard to clinically relevant abnormalities. The laboratory results should be signed and dated and retained at center as source data for laboratory variables. For information on how adverse events based on laboratory tests should be recorded and reported, see Section 6.3.

In case a patient shows an AST or ALT $\geq 3 \times$ ULN or total bilirubin $\geq 2 \times$ ULN please refer to [Appendix D](#) ‘Actions required in cases of combined increase of Aminotransferase and Total Bilirubin – Hy’s Law’, for further instructions.

5.2.2 Physical examination

A complete physical examination will be performed on Day -28, Day 22, Day 64, and ET and will include an assessment of the following: general appearance, respiratory, cardiovascular, abdomen skin, head and neck (including ears, eyes, nose, and throat), lymph nodes, thyroid, abdomen, musculo-skeletal (including spine and extremities), and neurological systems. A brief physical examination will be performed at Screening, Day -7, Day 1, Day 15, Day 57, Day 70, and at the follow-up visit and will include an assessment of the following: general appearance, sitting heart rate, sitting blood pressure, weight, and body temperature. Additionally the patient’s chief complaints will be obtained during the physical examinations.

5.2.3 Height, weight, and body mass index

Measurement of weight should be performed with the patient dressed in indoor clothing, shoes removed, and bladder empty. Patients should be weighed on the same scale at all visits.

Measurement of height should be performed with the patient’s shoes removed. The patient’s knees should be straightened, head held erect, and eyes forward.

Body mass index is used as an index of obesity and is a method of defining normal body weight and excess body fat. It correlates in a population with percent body fat.

Body mass index is determined by weight (kg) divided by height (m) squared.

Method of BMI Calculation:

- Use actual height and weight to calculate BMI.
- To calculate BMI:
 - Convert pounds to kilograms ($\text{kg} = \text{lb} / 2.2$)
 - Convert inches to centimeters ($\text{cm} = \text{in} \times 2.54$)
 - $\text{BMI} = (\text{weight in kg}) / (\text{height in cm}/100)^2$

Round to one decimal place (if .05 or greater, round up).

The BMI calculator provided by AstraZeneca may also be used to calculate BMI.

Additional calculations for BMI will be derived internally by AstraZeneca using the weight at the specified time point and the height at screening.

